### **Risks Associated With Fetal Exposure to ADs**

The following studies, though conflicting and methodologically limited, raise concern that prenatal AD use impacts risk for teratogenic outcomes, perinatal withdrawal symptoms, and obstetrical complications and have prompted clinicians and patients to avoid AD exposure during pregnancy.

## Partners Human Research Committee Detailed Protocol

Teratogenicity. Though recently more data have become available through several large birth defect surveillance programs, study limitations including small sample size, variation in outcomes reported, and inconsistent conclusions, have made using these sources to inform clinical decisions regarding pharmacologic management during pregnancy challenging for both patient and clinician. For example, two large case-control studies published recently questioned the safety of selective serotonin reuptake inhibitors (SSRIs) with respect to teratogenic risk using large records from a managed care organization and the Swedish Birth registry(25, 26). Based on their size, these studies might be expected to refine the risk estimate for congenital malformations following fetal exposure to SSRIs, but they produced divergent results.

The National Birth Defects Prevention Study compared 9,622 infants with birth defects with 4,092 control infants born in the United States from 1997 to 2003 and found no overall significant association between use of any SSRI in early pregnancy and congenital heart defects or most other birth defects analyzed. The exception was a significantly increased risk, particularly with paroxetine, for anencephaly (odds ratio 2.4), craniosynostosis (OR 2.5), and omphalocele (OR 2.8), birth defects that have not been associated with in utero exposure to SSRIs in previous studies(25). Yet in the accompanying data from the case-control Sloane Epidemiology Center Birth Defects Study (9,849 infants with birth defects and 5,860 infants without), no associations were identified between overall maternal SSRI use in early pregnancy and these three anomalies or congenital heart defects(26). There was, however, a significant association between paroxetine exposure and right-ventricular outflow tract obstruction defects (odds ratio of 3.3), as well as between the use of sertraline specifically and both omphalocele (odds ratio 5.7) and septal defects (2.0). It should be noted that the number of actual exposures in these studies to a specific SSRI was particularly small (<10). Thus, despite larger amounts of data which appear to be reassuring with respect to fetal exposure to SSRIs and risk for organ malformation, these inconsistent conclusions make patients and clinicians vigilant about use of ADs during pregnancy.

Recently, studies have raised concerns about whether prenatal AD use is associated with an increased risk of autism, although studies have been inconsistent in whether there is an increased risk or not among children who have been exposed to ADs in utero.

Perinatal Outcomes. Some(27-31), but not all(22, 32, 33)studies have noted an association between fetal exposure to SSRIs and adverse perinatal outcomes, including decreased gestational age, low birth weight, and poor neonatal adaptation, leading to increased rates of newborn complications and subsequent special care nursery admissions(27, 34-38). Several recent reports have noted an increased incidence of neonatal jitteriness, tachypnea, cyanosis, and tremulousness with late pregnancy exposure to SSRIs, while other studies have inconsistently reported an increased risk of persistent pulmonary hypertension of the newborn (PPHN)(27, 28, 34). While these associations deserve further study, the seriousness of the condition has led many women and their health care providers to attempt to discontinue AD prior to or during pregnancy. These analyses have led some authors to suggest AD discontinuation prior to delivery to presumably minimize the risk of neonatal toxicity. Additionally, FDA mandated labeling across the SSRIs also recommends discontinuation prior to delivery. While the recommendation is intuitive, the data are not conclusive and withdrawing treatment from patients just as they are about to enter the postpartum period, a time of heightened risk for affective illness, may carry significant clinical risk.

Although concerning, these studies vary greatly in the method of assessment, have limited blinded assessments, and include confounding factors such as other medication use or other psychological disorders and retrospective design, limiting their clinical significance. Moreover, research is required regarding if these short term symptoms have long-term effects.

Obstetrical Outcomes. Preterm birth (< 37 weeks gestation) is an obstetrical outcome of significant

## Partners Human Research Committee Detailed Protocol

clinical relevance, as it affects up to 15% of all births in the US and remains a leading cause of perinatal morbidity(39). Premature infants are more likely to suffer from cerebral palsy, respiratory difficulties, and learning difficulties than infants who are born at term(39, 40). In addition to emotional and social burdens to society, preterm birth poses significant financial burdens: in 2003 the March of Dimes reported that total hospital costs related to preterm birth were in excess of \$18 billion in the US(41). While the costs per case decrease with each advancing week of gestation, the number of preterm births increases, resulting in comparable total expenses for early and late preterm birth. Neonatal morbidity is most concerning with early preterm births; however recent studies have examined neonatal medical problems in premature infants between 35 and 37 weeks, and have found increased cases of temperature instability, hypoglycemia, respiratory distress, jaundice, evaluations for sepsis, and treatment with intravenous infusions(42).

Several studies have shown an association between fetal exposure to various medications and preterm birth(22, 33, 37, 43-47). Serotonin is a potent vasoconstrictor of the umbilicoplacental circulatory bed and circulatory levels of serotonin have been shown to be markedly increased in preeclampsia(48, 49). The net effect of most clinically available ADs is increased serotonin neurotransmission as well as alterations in beta-adrenergic receptors. Though all but one of these negative studies(35) included prospectively followed subjects, they were limited by the fact that AD exposure occurred only during early pregnancy for the majority of subjects(33, 37, 43-47), by small sample sizes(22, 32, 35, 38, 47, 50), and by the lack of a comparison unexposed control group(51). The exact mechanism by which ADs may impact pregnancy duration is not known.

### **Treatment Decisions during Pregnancy Are Not Driven by Illness Severity**

In a naturalistic prospective study, investigators found that over 43% of women discontinuing AD medications due to pregnancy concerns relapsed, over 50% during the first trimester(3). It could be expected that without random assignment to participation in the study, the participants who elected to enroll would be those with the least severe depression histories. This presumes patients with a history of multiple episodes would disproportionately choose to continue pharmacologic treatment, as compared to women with histories of fewer or more mild illness. However, data from a large scale, multi-site study conducted Cohen, et al. show that there is a broad distribution of AD use early in pregnancy in patients that is not wholly confounded with severity of illness as defined by number of episodes of major depression. We found no association between the decision to discontinue medication during pregnancy and duration of illness, number of previous episodes, or frequency of co-morbid psychiatric illness(3).

### **Selection of Intervention (EnBrace prenatal supplement)**

The current study will provide evidence regarding the efficacy, tolerability, feasibility and acceptability of a selected non-psychotropic treatment alternative to AD use while women are trying to conceive or during pregnancy. We hypothesize that rates of MDD relapse coinciding with AD discontinuation proximate to pregnancy may be attenuated if there are other effective treatments available to women.

### **Candidate Non-psychotropic Treatments for Women Trying to Conceive and During Pregnancy**

Ideally, a candidate treatment for MDD in pregnant women and those trying to conceive would: 1) demonstrate efficacy for MDD, 2) have a good safety profile in pregnancy and lactation, and 3) benefit the pregnancy beyond its impact upon MDD. The decision to continue an AD may be appropriate for some women who suffer from a history of highly recurrent disease, although most wish to have alternatives. Integrative, or Complementary and Alternative Medicine (CAM) treatments, have been increasingly used by individuals with MDD, particularly women, making the study of the efficacy of these interventions that much more compelling and urgent. Demonstrating the attractiveness of non-

## Partners Human Research Committee Detailed Protocol

psychotropic options, a recent report demonstrated that over 40% of the adult population in the U.S. used at least one CAM treatment over the past year, with women more likely than men to use CAM(52, 53). This pattern of utilization highlights the need for more research with integrative treatments for depression in women, as they are more likely than men to both suffer from MDD and to use CAM treatments(52). MDD is a common indication for nutritional supplement use, particularly among women, underscoring the attractiveness of these treatments to patients and the urgent need for systematic study of these interventions(54-58).

### **L-methylfolate and Other Folate-related Compounds**

There is consistent and growing evidence of a role for various folate forms in the prevention and treatment of depression. In fact, there is compelling evidence that treatment with a methylfolate agent would not only avoid the potential risks of ADs in pregnancy, but would also confer important benefits to pregnancy and child outcomes as well, such as prevention of congenital birth defects and longer term neurodevelopmental outcomes. To date, there is an evidence base for AD effects for folic acid, folinic acid, and methylfolate, and similar findings may be attributable to the fact that these folate forms share an interconversion potential in the complex set of pathways that comprise the one-carbon cycle(59-62). These reactions, which depend on B12 and homocysteine availability, are postulated to exert an AD effect by impacting the synthesis of neurotransmitters such as norepinephrine, dopamine, and serotonin.

Some but not all studies suggest efficacy of folate monotherapy for MDD, but this intervention may be limited by the common occurrence of polymorphisms in the general population that make folate a less efficient one-carbon cycle constituent than L-methylfolate. Since certain polymorphisms that impair methylation processes and the conversion of folate into its active form, methylfolate, have been found to be common in individuals with MDD, methylfolate may be a more effective form of folate supplementation to target MDD(63). Also, methylfolate may be more readily absorbed in the brain compared to other folate forms(64).

Recently, Fava and colleagues demonstrated that adjunct L-methylfolate is significantly superior to placebo for the treatment of MDD in patients who had failed to respond to AD therapy alone (65). In addition, several other open and blinded studies of methylfolate monotherapy in a variety of depressed populations have found that patients experienced significant improvement in depressive symptoms with no drug-related adverse events(66-70). Although more controlled data are needed, initial studies indicate that methylfolate may be a safe and effective option for the treatment of MDD, especially in populations that are vulnerable to medication-related adverse events, and those who are folate deficient or whose folate needs are elevated, such as pregnant women.

### **Omega-3 Fatty Acids, Depression, and Pregnancy**

**Omega-3 Fatty Acids:** Omega-3 fatty acids are nutritional compounds with well established benefits for human health, and particular benefits for fetal and infant development. Eicosapentaenoic acid (EPA) and docosahexaenoic acid (DHA) are two important omega-3 fatty acids found in fish and most fish oil or omega-3 supplements. The majority of randomized controlled trials demonstrate a significant AD benefit of omega-3 fatty acids in mood disorders overall, although they are best studied as an augmentation treatment rather than a stand-alone therapy.

**Perinatal Depression Considerations:** The benefits of maternal omega-3 fatty acid intake have been established for infant outcomes, although women are often afraid to eat fish during pregnancy since the U.S. FDA mercury advisories. Only a few treatment studies have specifically looked at omega-3 fatty

## Partners Human Research Committee Detailed Protocol

acids as a primary treatment for MDD during pregnancy and postpartum depression, and they have been small studies with mixed outcomes. Omega-3 fatty acid supplements have been well tolerated by pregnant and postpartum women. The exact dose still needs to be determined for optimal benefits for MDD, but modest doses of EPA and DHA (with a higher ratio of EPA:DHA) have shown the most promise, and is a reasonable dose for general health benefits, infant outcome benefits, and as an add-on treatment for MDD.

**EnBrace HR** is a prescription prenatal/postnatal dietary management product that contains vitamins and minerals, including folic acid and methylfolate. It meets the above criteria as a potential ideal candidate for the prevention of MDD in pregnancy. It contains L-methylfolate and other folate derivatives, and is optimal for a population with high rates of polymorphisms that affect folic acid metabolism. It also contains omega-3 fatty acids, primarily EPA, which shows promise for the treatment of depression. Importantly, these components are crucial for healthy pregnancies. Folic acid supplementation has been associated with the reduced risk of neural tube defects and is recommended for use in women of reproductive potential to reduce the risk of birth defects. Given that a substantial proportion of the population are poor folic acid metabolizers, methylfolate compounds may provide a more efficient delivery of folate-related compounds. Also, folate-related compounds supplemented in utero (folic acid, methylfolate) are associated with a lower risk of subsequent autism in children(71, 72).

### **Rationale behind research and potential benefits to patients and/or society**

Women who experience depression while trying to conceive and during a pregnancy often seek to minimize exposure to psychotropic medications. Likewise, women in remission from depression who are currently taking maintenance AD treatment and who are planning to conceive or are pregnant will often discontinue treatment out of concern over known and unknown risks of fetal exposure to these medications, regardless of clinical evidence showing that this puts them at a higher risk of relapse. The decision to avoid or discontinue maintenance AD treatment during pregnancy is also often made despite the risk of recurrence of MDD, which may result in a range of negative outcomes for both the mother and her newborn.

However, few studies have examined folate treatment specifically to assist patients who wish to avoid or discontinue ADs, and none have examined this during the time proximate to attempts to conceive, or during pregnancy, which is particularly relevant due to safety concerns. The adaptation of a non-psychotropic treatment for use in women who are pregnant or planning pregnancy who choose to avoid or discontinue maintenance AD treatment would broaden treatment choices available during this important time in the female life-cycle.

## **II. SPECIFIC AIMS**

### **a. Specify objectives and hypotheses to be tested**

**Objective:** The overarching goal of this investigation is to assess EnBrace as a treatment for the acute treatment and prevention of depression in women with a history of major depressive disorder who decide to avoid or discontinue their maintenance AD treatment for pregnancy. After completing this protocol, we plan to use the preliminary data for the development of a randomized controlled trial protocol. We will include two groups of women who are interested in minimizing medication exposures while trying to conceive or during pregnancy: 1) women who have histories of depression and are not depressed, and would like to stop antidepressants for pregnancy, 2) women in depressive episodes who are pregnant or trying to conceive (on or off of antidepressant medications).

**Specific Aim 1a:** To evaluate the efficacy of EnBrace when used as maintenance treatment for MDD in a group of women (N=10) who are trying to conceive or are early in pregnancy and who

## Partners Human Research Committee Detailed Protocol

have decided to stop ADs (Group 1). Relapse rates for women in this context have been demonstrated to be high, with 68% relapse rates in a large multisite NIMH-funded trial.

**Specific Aim 1b:** To evaluate the efficacy of EnBrace when used as an acute treatment for MDD in a group of women (N=10) who are trying to conceive or are early in pregnancy (Group 2). Women will have major depressive episodes in this group, and may receive EnBrace as monotherapy, or as an adjunct to current pharmacotherapy.

*Hypothesis 1a:* We hypothesize that relapse rates will be lower for women who receive EnBrace compared to historical controls. MDD relapse will be determined by the Mini-International Neuropsychiatric Interview (MINI) mood module that will be administered by a study clinician at each visit.

*Hypothesis 1b:* We hypothesize that the majority of women who receive EnBrace will experience a response (50% improvement in depressive symptoms) to EnBrace therapy.

**Specific Aim 2:** To identify biological markers as potential predictors of response to EnBrace.

*Hypothesis 2:* We hypothesize that pre- to post-treatment changes in homocysteine, folate, B12, IL-6 and CRP will be associated with response to EnBrace. We hypothesize specifically that levels of folate and B12 will increase and homocysteine will decrease temporally with treatment and be predictive of prevention of depressive episodes. We hypothesize that treatment will lower IL-6 and CRP levels due to the anti-inflammatory components of EnBrace (i.e., omega-3 fatty acids) and that decreased levels of inflammatory markers may predict lower risk of depressive relapse in participants who enter the study while not on a depressive episode (Group 1), and will predict response to treatment in women who enter the study while in a depressive episode (Group 2).

**Specific Aim 3 (Exploratory):** To identify factors influencing adherence to and tolerability of treatment. This will be achieved by using qualitative methods to explore (a) perceived risks and benefits of treatment; (b) perceived side effect profile; (c) treatment convenience; (d) knowledge of, attitudes towards, and preferences for depression treatment while attempting to conceive or early pregnancy.

*Hypothesis 3:* We hypothesize that EnBrace will be perceived by patients as 1) an acceptable and attractive treatment with a favorable risk/benefit profile in the context of pregnancy or while trying to conceive, 2) well tolerated, 3) convenient and easy to adhere to, 4) will be a treatment that women who are trying to conceive or who are pregnant find intuitive and preferable to prescription antidepressant medication (or for women on antidepressant treatment in Group 2, who prefer the augmentation with EnBrace rather than an increase in antidepressant dose or augmentation with a prescription psychotropic medication).

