## Partners Human Research Committee Detailed Protocol

1. Planning pregnancy or pregnant < 28 weeks gestation
2. Currently meet criteria for stable remission from MDD, defined as a baseline score of  $\leq 10$  on the Montgomery-Åsberg Depression Rating Scale (MADRS)
3. Current or recent treatment with an AD
4. Have elected to discontinue AD medication for pregnancy (may have already begun or completed taper)
5. Have a history of a major depressive episode/ Previous Episode of MDD, as verified using the MINI Structured Clinical Interview for DSM-5; have MDD as one of their primary diagnoses
6. Has a treating prescribing clinician for the treatment of MDD

**Exclusion Criteria:** The presence of any of the following criteria will exclude subjects from participation:

1. Current major depressive episode, as diagnosed on the MINI mood portion
2. Significant risk for self-harm or harm to others
3. Psychotic symptoms
4. Meeting criteria for a primary diagnosis of schizophrenia, an active eating disorder, dementia, delirium, or other cognitive disorder
5. Presence of an active substance and/or alcohol abuse disorder within six months prior to screening
6. Pernicious anemia or history of gastric bypass surgery
7. Seizure disorder and/or on anticonvulsant medications
8. Allergy to beeswax, soy, fish, nuts, peanuts, egg, wheat, milk, and/or shellfish
9. Non-English speaking

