**Schedule of Assessments: Acute Phase (12 weeks)**

Visit #	V1	V2	V3	V4	V5	V6	V7
Week #	0	2	4	6	8	10	12
MINI: full MINI at V1; depression module at follow-ups	X	X	X	X	X	X	X
Demographics, medical & psychiatric history	X						
Labs: genetic sample	X						
Labs: folate, homocysteine, B12, IL-6, CRP	X			X			X
Vital Signs: Height only at V1, weight, blood pressure	X	X	X	X	X	X	X
MADRS	X	X	X	X	X	X	X
CGI-Clinician	X	X	X	X	X	X	X
EPDS	X	X	X	X	X	X	X
QIDS-SR	X	X	X	X	X	X	X
Q-LES-Q-SF	X			X			X

A Qualitative interview will be conducted by study staff after completion of the acute treatment phase in order to obtain feedback on the intervention.

Instrument Descriptions:

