## V. BIOSTATISTICAL ANALYSIS

We will compare the rates of depressive relapse and duration of time out of a depressive episode for Group 1 participants, and compare these data to historical controls that were also assessed prospectively. For Group 2, we will compare depressive response rates (response defined as 50% reduction in depressive symptoms on the MADRS, our primary outcome) to response rates in studies of SSRIs for the treatment of depression.

In addition, we will monitor depressive symptom burden with continuous variables across the treatment study for both groups.

To control for prenatal vitamin (PNV) use, we will supply a standard PNV to each participant to take daily in combination with EnBrace. The Sponsor has offered to supply the PNV, such that each participant will take the same PNV; this will lower the risk of inconsistencies between participants. In the statistical analysis, the data collected in this preliminary study will be compared to historical controls with a history of MDD who discontinued AD maintenance therapy during pregnancy, most of which were taking standard PNVs, but not EnBrace. This reference will allow us to estimate the relative efficacy of EnBrace in relapse prevention of women who discontinue maintenance ADs for pregnancy.

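### The Group 1 comparison with historical discontinuers sets no common follow-up window or time origin, so a relapse rate below 68% could reflect the shorter window rather than the product

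*Combined protocol and SAP*

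**What the plan says.** Section II (Specific Aim 1a) sets out to evaluate efficacy as maintenance treatment in 10 women and gives one historical figure: "Relapse rates for women in this context have been demonstrated to be high, with 68% relapse rates in a large multisite NIMH-funded trial". Hypothesis 1a predicts lower relapse than in historical controls, with relapse determined by the MINI mood module at each visit.

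Section V says the team will "compare the rates of depressive relapse and duration of time out of a depressive episode for Group 1 participants" and set the results against prospectively assessed historical controls. It describes the data as being "compared to historical controls with a history of MDD who discontinued AD maintenance therapy during pregnancy", and adds: "This reference will allow us to estimate the relative efficacy of EnBrace in relapse prevention of women who discontinue maintenance ADs for pregnancy". It names no comparator rate, follow-up length, time origin or censoring rule. It does not itself name 68%; that link comes from Aim 1a.

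The only schedule of assessments has visits every two weeks from week 0 to week 12. Section III defines who is at week 0 in Group 1:

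- Reproductive stage: "Planning pregnancy or pregnant < 28 weeks gestation".
- Antidepressant status: "Have elected to discontinue AD medication for pregnancy (may have already begun or completed taper".
- Excluded: "Current major depressive episode, as diagnosed on the MINI mood portion".

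The Background repeats the 68% as relapse among women who stopped antidepressants, in a paragraph on relapse during pregnancy, again with no follow-up length. The subsection on treatment decisions and illness severity, citing the same reference, says that more than half relapsed in the first trimester.

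**The concern.** Group 1 has no concurrent control, so the historical comparison is its entire efficacy analysis. A cumulative relapse proportion means little without the period over which it accumulated and the point from which it was counted. For Group 1 the period is 12 weeks and the origin is enrolment. For the controls neither is stated.

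Enrolment is also not a fixed point in the course of discontinuation. A woman who has not begun her taper may spend part of the 12 weeks on an antidepressant. A woman who has completed it has already stayed well long enough to qualify. Some Group 1 women are not yet pregnant, whereas the controls stopped during pregnancy. The second endpoint, time out of episode, has the same gap: a duration needs an origin and a censoring rule, and in Group 1 it cannot exceed 12 weeks.

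At stake is whether a difference produced by unequal windows is reported as relative efficacy and then carried into the randomised trial that Section II says these data will help to develop.

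**Working it through.** There is no figure of the plan's to reproduce: the documents contain no sample-size, power or significance calculation, and the 68% is cited, not derived.

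**Inputs from the documents.** n = 10 and 68% (Section II); 12 weeks (schedule of assessments).

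**Assumption, not in the documents.** A share f of the relapses behind the 68% falls within 12 weeks.

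**Step 1: 12-week rate with no product effect.** p12 = 0.68 × f; expected relapses = 10 × p12.

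**Step 2: chance of a low count with no product effect.** P(X ≤ 3) = Σ C(10,k) p12^k (1 − p12)^(10−k), k = 0 to 3. Three is used because it is the largest count that would look clearly lower than 68%: at p = 0.68, P(X ≤ 3) = 0.0155 and P(X ≤ 4) = 0.0637. The plan sets no such cut-off; it is used here only to show size.

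| f | p12 | expected in 10 | P(X ≤ 3) |
|---|---|---|---|
| 0.5 | 0.340 | 3.4 | 0.541 |
| 0.6 | 0.408 | 4.1 | 0.362 |
| 0.7 | 0.476 | 4.8 | 0.214 |
| 0.8 | 0.544 | 5.4 | 0.109 |
| 1.0 | 0.680 | 6.8 | 0.016 |

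The last row is the case with no window distortion.

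**Step 3: a different assumed shape.** With a constant hazard and the 68% accrued over T weeks, p12 = 1 − 0.32^(12/T). T = 24 gives 43.4% and P(X ≤ 3) = 0.30; T = 40 gives 29.0% and 0.68.

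**Step 4: the nearest timing clue.** The Background's first-trimester remark is ambiguous. As a share of relapses, it puts the no-effect rate above 0.68 × 0.50 = 34%. As a share of discontinuers, it puts it above 50%, that is f > 0.50/0.68 = 0.735. Both readings treat the first trimester as equal to the 12-week window. Both are lower bounds only.

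**Step 5: precision.** An observed 3/10 has an exact 95% CI of 6.7% to 65.2%. This excludes 68% but contains the whole range 34% to 54%, so the same result supports opposite readings depending on the benchmark. Against 34%, only 0/10 (upper limit 30.8%) has an interval wholly below; 1/10 reaches 44.5%.

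**Step 6: episode-free entry, as a possibility only.** If a share g of the 68% occurs before the point at which a woman enrols, the rate among those still well is 0.68(1 − g)/(1 − 0.68g): 65.7%, 61.4% and 51.5% for g = 0.10, 0.25 and 0.50. This matters only if the controls were counted from an earlier point, which the documents do not say.

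**The case against.** The strongest reply is that the direction of bias is not established. The documents never state the historical follow-up. Nor do they say that the controls entered in an episode or were counted from discontinuation, and the word relapse itself presupposes having been well. Women who have not begun taper lose no post-discontinuation relapses before entry. All of this stands. Enrolment close to taper could even raise Group 1's rate relative to a historical window that starts later, so the effect of differing origins has no known sign.

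A reader might therefore infer too much in three ways: that 68% is the plan's declared benchmark, that the comparison is known to favour the product, or that episode-free entry by itself lowers Group 1's expected rate. Section V does not name 68%, and the other two inferences depend on facts about the controls that are not given.

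It can also be said that this is a preliminary study with no success threshold or decision rule, and that at N=10 alignment changes interpretation more than inference. That limits the consequence. It does not remove it, because Section V still promises an estimate of relative efficacy. Prospective assessment of the controls addresses how relapse was detected, not the window or origin.

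The Background also cites the same reference for a discontinuer relapse figure of over 43%, without reconciling it with 68%. That is a separate wording point and adds no weight here.

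**Conclusion.** The omission is real and should be fixed. The plan's only efficacy analysis for Group 1 compares a 12-week rate, counted from a variable entry point, with a historical rate whose window and origin are unstated.

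The size cannot be determined from the documents. If the 68% accrued over more than 12 weeks, a lower Group 1 rate is expected with no product effect. With 50% to 80% of relapses assumed to fall within 12 weeks, 3.4 to 5.4 relapses in 10 are expected instead of 6.8, and the chance of 3 or fewer is 54% to 11%. If all of the 68% fell within 12 weeks, the window causes no distortion. A longer historical window is suggested by the pregnancy setting of the 68% and by the first-trimester remark, but it is not stated. The documents do not support a claim that the comparison is certainly biased towards the product.

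**What to change.** In Hypothesis 1a and Section V, state the following.

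- **Comparison.** Group 1's relapse over 12 weeks from enrolment, with an exact 95% CI, will be compared descriptively with the historical discontinuers' relapse over a 12-week window that starts from a relapse-free state at a similar time since discontinuation. Time out of episode will use the same origin and window.
- **Stage.** Match on gestational stage only for women pregnant at entry. Report women still planning pregnancy separately, without a matched control.
- **Early leavers.** Withdrawals under drop criteria 1 (severe worsening) and 4 (which includes emergent suicidal ideation) must not be treated as non-informative censoring, since that would count the worst courses as non-events. Count them as relapse, or show a sensitivity analysis that does. State how other early leavers, including women who restart an antidepressant while well (criterion 2), enter the proportion.
- **Fallback.** If matched data cannot be obtained, state that no efficacy conclusion will be drawn against 68%.

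The cost is wording; no patients or visits are added. The matched comparison needs historical time-to-relapse data. The team may hold them: the Background presents the cited study's findings as its own, Section V plans a time-based comparison, and Section VI mentions the team's Prospective Pregnancy Study (n=201). The documents do not confirm access, or that this is the same cohort. The downside is a probably less favourable benchmark and a comparison that stays imprecise and descriptive at N=10.
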